2. TRIAL RATIONALE

2.1. Relevance of the trial

Acute cerebral circulatory disorders (ACCD) are a problem of great medical and social importance due to the significant frequency of their development, high rate of disability and mortality [Evzelman M. A. and Alexandrova N. A., 2013]. Stroke includes ACCD, characterized by the sudden (within minutes, less often - hours) appearance of focal neurological symptoms (motor, speech, sensory, coordinator, visual and other disorders) and/or general cerebral disorders (changes in consciousness, headache, vomiting, etc.), which persist for more than 24 hours or lead to the death of the patient in a shorter period of time due to the cause of cerebrovascular origin [Vereshchagin N. V. et al., 2002].

The annual stroke mortality rate in Russia is one of the highest in the world (175 cases per 100,000 population per year). According to the National Stroke Association register, 31 per cent of stroke patients require assistance to care for themselves and 20 per cent are unable to walk independently. Residual phenomena after stroke are detected in about 2/3 of patients, of which 50% - cognitive impairment, which limits social adaptation, including labour activity and self-care in the home, even in the absence of significant motor impairment [Evzelman M. A. and Alexandrova N. A., 2013; Stakhovskaya et al., 2012].

The most common in clinical practice is ischaemic stroke (IS) - ACCD, accompanied by

damage to brain tissue, impairment of its functions due to obstruction or cessation of blood flow to one or another part [Evzelman M. A. and Alexandrova N. A., 2013]. According to the register of brain stroke, conducted by the Research Institute of Neurology RAMS (Scientific Centre of Neurology), by the end of the acute period (3 weeks from the onset of the disease) hemiparesis is observed in 81.2% of surviving patients, including hemiplegia - 11.2%, arthropathy - 15-20%, aphasia - 35.9%, dysarthria - 13% [Fedin A. I. et al., 2009].

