Telephone visit 2 (Day 55±2 from initiation of therapy; Day 45±2 from initiation of oral therapy):

The investigator should contact the patient by telephone to assess concomitant therapy, to record AE and assess exclusion criteria, and to assess compliance.

Visit 4 (day 71(+2) from start of therapy; end of therapy)

The visit is conducted in the context of the patient's outpatient visit to the investigational site and includes the following procedures:

- physical examination,
- neurological examination,
- assessment of vital signs (BP, HR, respiratory rate, body temperature),
- evaluation of concomitant therapy,
- AEs registration;
- evaluation of exclusion criteria;
- clinical blood test,
- blood chemistry;
- urinalysis;
- pregnancy test for women with preserved reproductive potential,
- ECG
- completion of specialised scales and calculation of indices (mRS, NIHSS, HADS, MoCA, Rivermead mobility index),
- IP take-back and compliance assessment

Additional in-person/out-person (phone calls) visits may be conducted if necessary in the reasonable judgement of the investigator, particularly to monitor the progression of SAEs. The scope of activities and procedures performed at additional visits will be determined by the investigator on an individual basis, depending on the indications.

In case of early withdrawal of a patient from the trial, a Visit to End Patient Participation in the Trial is performed, including activities identical to those of Visit 4.

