6.3.11. Patient assessment using specialised scales

Conducted according to the trial procedure schedule to assess the patient's condition for subsequent analyses of therapy efficacy using the following scales:

- mRS (Modified Rankin Scale) - score on Visits 0, 2, 4;
- NIHSS (The National Institutes of Health Stroke Scale) - score on Visits 0, 2, 4;
- Montreal Cognitive Assessment Scale MoCA - score on Visits 1, 2, 4;
- Hospital Anxiety and Depression Scale (HADS) - scores on Visits 1, 2, 4;
- Rivermead Mobility Index - score on Visits 1, 2, 4.

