11.8. Compliance with the Protocol

The Investigator shall conduct the trial in accordance with the approved Protocol.

A deviation from the Protocol is any change, inconsistency, or departure from the trial design or procedures of the Trial Protocol.

Any deviation from the Protocol during the conduct of a clinical trial must be recorded and reflected in the trial documentation.

All deviations from the Protocol are categorized into major deviations and minor deviations.

Minor deviation from the protocol - does not significantly affect the rights, safety and welfare of the patient or the completeness, accuracy and reliability of the trial data.

A significant protocol deviation (or protocol violation) is a deviation that may affect the rights, safety and welfare of the patient or the completeness, accuracy and reliability of the trial data.

Examples of significant deviations from protocol:

- patient met the exclusion criteria for the trial but was not excluded;
- patient has received a prohibited concomitant therapy drug;
- patient was included in the trial although he/she did not fulfil the selection criteria;
- performing trial procedures without obtaining written informed consent from the patient;
- violations of the procedure of IP administration by the patient (prescribing to one patient an IP with different randomization codes, inconsistency of labelling and randomization code in the source documentation, CRF, on all types of product packaging and in the patient registration and dispensing logs of the investigational product);
- patient indiscipline, failure to comply with restrictions during participation in the trial;
- systematic (repeated at least 2 times) negligent loss at a investigational site of data or samples collected for trial; and the negligent loss of data or samples collected for trial at a investigational site;
- skip of visits.

Major deviations must be reported to the ethics committee. If major deviations from the protocol are found, the patient should be excluded from the final analysis of efficacy data.

In the event that the visit procedures exceed the timeframes outlined in this protocol, the possibility of the patient's continued participation in the trial will be considered by the Sponsor, at the request of the investigator, on a case-by-case basis.

11.9.Final trial report

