APPENDIX 2.

mRS (Modified Rankin Scale)

Example form

Tick only one box

- Complete absence of symptoms (0 points)
- No significant disability despite the presence of symptoms: the patient can perform all his/her daily duties and activities (1 point)
- Mild incapacity: the patient is unable to perform his/her usual work, but is capable of self-care without assistance (2 points)
- Moderate disability: sometimes requires assistance but can walk independently (3 points)
- Moderately severe disability: the patient cannot walk unaided and is unable to perform self-care without assistance (4 points)
- Severe disability: patient is bedridden, incontinent of urine and faeces, needs constant care (5 points)
- Death (6 points)

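### The Day 71 mRS is scheduled only at an outpatient site visit with no written off-site fallback, so a patient too disabled to attend is likely to have no primary outcome

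*Protocol*

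**What the plan says.** **Where and when the score is taken.** Protocol 6.3.11 lists "mRS (Modified Rankin Scale) - score on Visits 0, 2, 4". Visit 4 is the only one of these at the end of therapy, and section 6.2 says of it: "The visit is conducted in the context of the patient's outpatient visit to the investigational site and includes the following procedures". The two telephone visits (Days 24 and 55) and Visit 3 (Day 40) carry no mRS (6.2, Appendix 1). No home, telephone, video or caregiver scoring is described.

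**What happens if the visit is missed.** Section 11.8 gives missed visits as an example of a significant deviation and continues: "If major deviations from the protocol are found, the patient should be excluded from the final analysis of efficacy data". Section 9.3 is narrower: a significant deviation that may affect the efficacy assessment removes the patient from the PP population. PP is the primary population, with ITT and mITT as additional analyses (9.7.2). Missing data are not filled in (protocol 9.4, SAP 11).

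**Other routes to a score.** Section 6.2 allows unscheduled contacts: "Additional in-person/out-person (phone calls) visits may be conducted if necessary in the reasonable judgement of the investigator", and "The scope of activities and procedures performed at additional visits will be determined by the investigator on an individual basis, depending on the indications". Section 5.4.4 has the investigator contact a treated patient who is withdrawn for a reason other than an adverse event, including non-attendance for an unknown reason, and book an end-of-trial visit. Section 6.2 gives the early-withdrawal visit the same activities as Visit 4, so it includes the mRS; its place is not stated. Section 11.8 refers out-of-window procedures to the sponsor case by case.

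**The concern.** The endpoint measures disability, and its only scheduled end-of-therapy assessment requires the patient to come to the site. Patients enter with mRS 3 or more and NIHSS 9 to 15 (5.1). In Appendix 2, grade 4 is a patient who cannot walk unaided, and grade 5 reads "Severe disability: patient is bedridden, incontinent of urine and faeces, needs constant care (5 points"). It is reasonable to expect these patients to be the hardest to bring in about two months after the inpatient Visit 2. If so, whether the outcome is observed depends on its value, and neither PP nor ITT without imputation restores the missing score. The primary comparison can then be biased, and the end-of-therapy proportion with mRS 3 or more (a secondary endpoint) can be understated.

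**Working it through.** **1. The plan's own sample size.** Inputs from protocol 9.1: expected difference 0.292, margin 0.027, SD 0.802, one-sided α 0.05, power 80%.

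n per arm = 2 × (1.6449 + 0.8416)² × 0.802² / (0.292 − 0.027)² = 113.25, rounded up to 114; two arms give 228; 228 / 0.75 = 304. The stated figures reproduce, and the implied attrition allowance is 25% (76 of 304).

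**2. Loss unrelated to outcome.** Power = Φ((difference − 0.027) / (0.802 × √(2/n)) − 1.645), with n the average number analysed per arm.

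| Loss | n per arm | Power |
|---|---|---|
| 0% | 152 | 89.2% |
| 10% | 136.8 | 86.2% |
| 25% | 114 | 80.2% |

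The allowance therefore covers lost precision. It does not cover loss that depends on the outcome.

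**3. Loss that depends on disability (illustration).**

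- From the documents: mean changes 2.278 (active) and 1.986 (placebo) from section 9.1. Shares with mRS 3 or more at end of therapy in the earlier trial (2.3.2): 59 of 61 and 53 of 63 reached 0–2, leaving 2/61 = 3.3% and 10/63 = 15.9%.
- Assumed: disabled patients improve 1.5 points less than the others; 10% of non-disabled patients lose the score; 40% or 60% of disabled patients lose it.

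For an arm with mean m, disabled share p and disabled loss q, the non-disabled mean is m + 1.5p. The observed mean is (m + 1.5p) − 1.5 × p(1 − q) / [p(1 − q) + 0.9(1 − p)].

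With q = 40%:

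- Active: 2.278 + 0.049 = 2.327; 2.327 − 1.5 × 0.0197/0.8902 = 2.294.
- Placebo: 1.986 + 0.238 = 2.224; 2.224 − 1.5 × 0.0952/0.8524 = 2.056.
- Difference 0.238. Analysed: 152 × (0.890 + 0.852) ≈ 265.

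| Disabled lost | Difference | Analysed | Power |
|---|---|---|---|
| 10% (same as others) | 0.292 | 274 | 86% |
| 40% | 0.238 | 265 | 69% |
| 60% | 0.197 | 259 | 52% |

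The shift comes from about 9 or 15 additional lost patients (274 − 265, 274 − 259), well inside the 25% allowance.

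Consistency check: a 1.5-point gap implies an SD of at least 1.5 × √(0.159 × 0.841) = 0.55 in placebo and 1.5 × √(0.033 × 0.967) = 0.27 in active. Both lie below the stated 0.847 and 0.755, so the scenario is compatible with section 9.1.

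**4. Other scenarios, same 1.5-point gap and 10% loss among the non-disabled.**

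- Disabled shares of 20% (active) and 30% (placebo), with 40% or 60% of disabled lost: difference 0.261 or 0.232, power 75% or 62%.
- Disabled share of 30% in both arms and equal loss: difference stays 0.292, no bias.
- Equal shares of 10–30%, with 30–50% of disabled patients lost in one arm only: 0.32 to 0.45 if that arm is active, 0.26 to 0.13 if it is placebo.

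**The case against.** The plan is less bare than it may look. The end-of-participation visit in 5.4.4 and 6.2 includes the mRS, and its place is left open. Extra contacts can have any scope the investigator chooses. An outpatient visit need not mean walking in, and assisted transport is not ruled out. In the earlier trial 141 of 150 randomised patients completed (2.3.2). No document figure shows who misses visits. Part of the loss also comes from choosing PP as primary and not imputing, which are separate matters.

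Much of this stands, and it limits the point in four ways where a reader might infer more.

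- *That the Day 71 score can be obtained only at the site.* The text supports only that it is scheduled there. The other routes may yield a score, but none is stated to count as Visit 4 or to keep the patient in PP.
- *That a missed visit removes the patient from every efficacy analysis.* This is certain for PP only: 11.8 speaks of efficacy analysis in general, 9.3 of PP. A patient with no score still has no change value in ITT.
- *That a fifth of these patients will be unable to walk at Day 71.* Section 2.1 does say "20 per cent are unable to walk independently", but this is a register figure for stroke patients in general, with no time point, arm or eligibility limit. It also cannot be paired with zero change in those patients. With a placebo mean of 1.986 the rest would average 1.986/0.8 = 2.48, which forces an SD of at least √(0.2 × 0.8) × 2.48 = 0.99 against the stated 0.847.
- *That the effect is bound to be understated.* Step 4 shows no bias, understatement or overstatement, depending on the shares and the losses by arm.

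Remote scoring also has a weakness: it would fall mainly on the most disabled patients, so mode and outcome are entangled. A remote mRS alone may not secure PP status either, because compliance is counted from dispensed and returned medication at Visits 3 and 4 (6.3.9).

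**Conclusion.** The gap is real and modest. The plan schedules its primary outcome only at an outpatient site visit, writes down no off-site method, and does not impute a missing score. A patient too disabled to attend is therefore likely to have no primary outcome in PP or ITT.

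That such patients miss more visits is an inference from the Appendix 2 grades. The difference of about 0.24 or 0.20 and power of about 69% or 52% are illustrations. They rest on the assumed 1.5-point gap and loss rates, and on shares from the earlier trial's per-protocol set, whose entry range (NIHSS 5–20) and dose differ from this trial's. Those shares also count mRS 3 patients, who can walk. They are combined here with ITT means.

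**What to change.** - **6.2 (Visit 4) and 6.3.11:** if the patient cannot travel to the site, the same blinded investigator scores the mRS on Day 71(+2) by telephone or video with the patient or caregiver, using the Appendix 2 grades, and records the mode in the eCRF.
- **11.8:** state that a Visit 4 mRS obtained this way is not a skipped visit. The score then enters ITT, and also PP when the other per-protocol conditions, including compliance, are met.
- **11.8 and 9.3:** reconcile exclusion from the efficacy analysis with exclusion from PP only.
- **SAP section 9:** add a sensitivity analysis that excludes the remote scores.

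This should not be extended to excuse a missed Visit 3, where oral medication is dispensed and compliance is counted.

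Cost: a short amendment, one eCRF field and one extra analysis, using site staff who already make the Day 24 and Day 55 calls. The downside is a small mode difference concentrated in the more disabled patients; the recorded mode and the sensitivity analysis make it visible but do not remove it.

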6.3. Description of the trial procedures

6.3.1. Obtaining written Informed Consent

Before any procedures provided at Screening will be performed, the patient (or his/her legal representative if the patient is not physically able to sign) must sign and date, in duplicate, the Patient Information Sheet with the Informed Consent Form for participation in the trial.

If the subject or his/her legal representative is unable to read, a disinterested witness may be present throughout the explanatory interview. After the written Informed Consent Form and other written materials provided to the subject have been read and explained to the subject or the subject's legal representative and the subject or the subject's legal representative has given

verbal consent for the subject's participation in the trial and, if able, has signed and dated the written Informed Consent Form, the witness must sign and date it. By signing the written Informed Consent Form, the witness certifies that the information contained in the form and all other written materials has been accurately explained and understood by the subject or his or her legal representative and that consent to participate in the trial has been given voluntarily by the subject or his or her legal representative.

The patient must be informed in writing:

1. On the medicinal product for human use and the essence of a clinical trial of this medicinal product;
2. On the safety of a medicinal product for human use and the degree of risk to the patient;
3. On the conditions for patient participation in a clinical trial of a medicinal product for human use;
4. On the purpose, objectives and duration of a clinical trial of a medicinal product for human use;
5. On the patient's actions in case of unexpected effects of a medicinal product for human use on his/her health condition;
6. On the conditions of compulsory insurance of the patient's life and health;
7. On guarantees of confidentiality of patient participation in a clinical trial of a medicinal product for human use.

The Investigator also signs and dates the Patient Information Sheet with the Informed Consent Form, thereby certifying that the interview with the patient was conducted and consent obtained, and that the patient had the opportunity to ask questions and received full answers.

The patient will receive one copy of the Patient Information Sheet with the Informed Consent Form and the second copy will be kept by the Investigator at the investigational site together with other trial documentation.

6.3.2. Medical history

During the screening (Visit 0), a detailed medical history will be collected from the patient: diseases suffered in the last year, comorbidities, surgical interventions, previous (in the last 4 weeks) and concomitant therapy, history of alcohol, medication and/or drug dependence, information about harmful habits (smoking and alcohol intake).

6.3.3. Demographic data and anthropometrics

Demographic data (date of birth, gender, race) will be obtained at the time of screening (Visit 0). Obtaining anthropometric data (body weight (to tenths of a kilogram), height, BMI) is provided at screening (Visit 0).

6.3.4. Physical examination

The physical examination will be performed by the Investigator at Visits 0-4 in accordance with the schedule of trial procedures.

Organs and systems whose condition is assessed during the examination:

- Skin and visible mucous membranes.
- Endocrine system.
- Lymphatic System.
- ENT organs.
- Respiratory system.
- Cardiovascular system.
- Gastrointestinal tract.
- Nervous system.
- Musculoskeletal system.

- Reproductive system.
- Urinary system.

6.3.5. Neurological examination

A neurological examination is performed at screening (Visit 0) and Visits 2 and 4 according to the trial procedure schedule to further assess neurological changes in the patient's condition.

6.3.6. Vital signs

To ensure patient safety, vital signs will be assessed by the Investigator at Visits 0-4 according to the trial procedures schedule.

Vital signs (BP, HR, RR) are measured after a 5-minute rest, if possible in a sitting position. BP (systolic and diastolic) will be determined on the right arm using a validated device. HR is assessed over a 1-minute period.

Axillary temperature will be measured to determine body temperature.

6.3.7. Electrocardiogram

ECG examination in this trial will be performed in 12 leads (I, II, III, aVR, aVL, aVF, V1 - V6) at Visits 0, 2, 4.

The ECG will be recorded for a time sufficient for evaluation (up to 10 seconds) after the patient has been at rest for a minimum of 10 minutes.

The HR will be measured and an opinion will be given as to whether the patient's ECG is normal, clinically significant or clinically insignificant.

At Visit 0, if data are available for a patient from an ECG examination performed within 48 hours prior to the patient's inclusion in the trial, these can be used to assess the patient's status and eligibility for inclusion/non-inclusion. A repeat ECG on Visit 0 is not required in this case.

